14 MEASUREMENT OF EFFECT

Definitions:

Response and progression will be assessed according to modified International Working Group (IWG) MDS/MPN criteria (see section 14).

Complete Response (CR)

1. Bone Marrow:
 - a. $\leq 5\%$ myeloblasts and promonocytes
 - b. \leq grade 1 reticulin fibrosis
2. Peripheral Blood:
 - a. $\text{WBC} \leq 10 \times 10^9$ cells/L
 - b. $\text{Hgb} \geq 11$ g/dL
 - c. $\text{Platelets} \geq 100 \times 10^9$ cells/L
 - d. Blasts 0%
 - e. Neutrophil precursors $\leq 2\%$
 - f. $\text{Monocytes} \leq 1 \times 10^9$ cells/L
3. Extramedullary Disease
 - a. Complete resolution of extramedullary disease present before therapy including palpable hepatosplenomegaly

Complete Cytogenetic Response

Resolution of previously present chromosomal abnormalities as seen on G band cytogenetics.

Partial Response

Normalization of peripheral counts and hepatosplenomegaly with bone marrow myeloblasts reduced by 50% but remaining $>5\%$ of cellularity except in cases of MDS/MPN with $\leq 5\%$ bone marrow blasts at baseline

Marrow Response

Optimal marrow response: Presence of all CR marrow criteria without normalization of peripheral blood indices.

Partial marrow response: Bone marrow blasts reduced by 50% but remaining $>5\%$ of cellularity **or** reduction in grading of reticulin fibrosis from baseline on at least 2 bone marrow evaluations at least 2 months apart.

Clinical Benefit

Requires 1 of the following in the absence of progression or CR/partial response and independent of marrow response to be considered clinical benefit.

1. Erythroid Response: a) Hgb increase by ≥ 2.0 g/dL b) TI for ≥ 8 wk for patients requiring at least 4 packed red blood cell transfusions in the previous 8 wk
Only red blood cell transfusions given based on physician's judgment for a pretreatment Hgb of ≤ 8.5 g/dL will count in the red blood cell TI response evaluation
2. Platelet response: a) Transfusion independence when previously requiring platelet transfusions of at least a rate of 4 platelet transfusions in the previous 8 wk. b) Pretreatment $\leq 20 \times 10^9$ /L: increase from $< 20 \times 10^9$ /L to $> 20 \times 10^9$ /L and by at least 100% c) Pretreatment $> 20 \times 10^9$ /L but $\leq 100 \times 10^9$ /L: absolute increase of $\geq 30 \times$

$10^9/L$

3. **Neutrophil response:** a) Pretreatment $\leq 0.5 \times 10^9/L$ at least 100% increase and an absolute increase $> 0.5 \times 10^9/L$ b) Pretreatment $> 0.5 \times 10^9/L$ and $\leq 1.0 \times 10^9/L$. At least 50% increase and an absolute increase $\geq 0.5 \times 10^9/L$
4. **Spleen response:** A $\geq 35\%$ reduction in spleen volume as measured by CT-scan from baseline at week 16.
5. **Symptom response:** Improvement in symptoms as noted by decrease of $\geq 50\%$ as per the MPN-SAF TSS scoring in those with a MPN-SAF TSS ≥ 17 (modified from original MDS/MPN-IWG).

Pathologic Response: Pathologic response is categorized as per the modified MDS/MPN IWG. Response parameters in the peripheral blood and/or bone marrow must be sustained for at least 4 weeks. See section 14.

Symptom Assessment in CMML

Symptoms of CMML will be assessed using the MPN-SAF TSS (see Appendix C). Patients will be issued a hand-held device (eDiary) on which to record symptoms of CMML. The subject will be instructed to complete the eDiary each night beginning on Day -4 or earlier of the screening phase (eg, 4 days prior to Cycle 1 Day 1) through treatment discontinuation. Patients will bring the device to the study site at each study visit so that the device charging can be verified and accumulated data can be downloaded, as applicable. The device will then be returned to the subject at these same visits for continued use each night. The subject will return the device and the docking station for the final time at the EOT visit so that the data can be archived. Detailed directions for the administration of the eDiary will be provided in the Study Reference Manual.

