13.1 Baseline Assessment: within 4 weeks of starting treatment

- Medical history including:
 - Disease characteristics such as date of diagnosis of CMML, WHO/FAB subtype, IPSS score, MD Anderson Scoring System (MDASC), prior treatments.
 - ECOG performance status.
- Concurrent medication review.
- Red blood cell and platelets transfusion past 8 weeks.
- Routine physical examination to include vital signs, height and weight.
- Bone marrow examination, including cytomorphology, cytogenetic assessment, and flow cytometry analysis. Possibly include NGS myeloid panel (it is not considered a deviation if cytogenetic, flow cytometry and NGS myeloid panel is not completed).
- Laboratory assessments:
 - Hematology to include platelet count, hemoglobin, hematocrit, white blood cells (WBC) and WBC differential (including: neutrophils, eosinophils,

basophils, lymphocytes and monocytes), INR, PT, and PTT and reticulocyte count.

- Clinical chemistries including BUN/urea, creatinine, chloride, sodium, potassium, alkaline phosphatase, alanine aminotransferase (ALT), aspartate aminotransferase (AST), total bilirubin, bicarbonate, calcium, chloride, glucose, LDH, total protein, and albumin.
- Urine or serum pregnancy test for females of childbearing potential will be performed at Screening or on Day 1, prior to first dose study medication.
- Symptom Score using the Myeloproliferative Neoplasms Symptom Assessment Form (MPN-SAF). (See Appendix C).
- CT scan of the abdomen to evaluate spleen volume.
- Review and record any blood and blood supportive care products for the prior 8 weeks.

Re-screening

Bone marrow biopsy and CT scan of the abdomen may not need to be repeated for a re-screening process if they are completed within 3 months from the time of consenting on the study. Although, all the other procedures including labs, Myeloproliferative Neoplasms Symptom Assessments, research labs (research lab exclude aspirate) will be performed during the re-screening process within 4 weeks prior to the start of the study treatment.

Patient can be re-screened and start the first day of treatment on the same day if patient meets the eligibility criteria on the study.

13.2 Treatment Period (weeks 1-16):

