- 13.2.1 Ruxolitinib will be administered as a twice daily oral dose for a 4-week treatment cycle. Patients will have a CBC with leukocyte differential performed weekly for the first 16 weeks. Serum chemistry will be performed weekly for first 4 weeks and then every 2 weeks through week 16. A BM aspirate and biopsy with cytogenetic analysis will be performed after cycle 2 and 4 (at the end of week 8 and week 16) to assess pathologic response, cytogenetic response and disease progression. For patients who achieve CR, marrow CR, or PR a confirmation bone marrow aspirate and biopsy should be obtained 4 to 8 weeks after documentation of CR, marrow CR, or PR.

13.3 **End of C4/ Week 16 Response Assessment:** Patients will complete a response assessment (see Section 14) within one week after their last administration of ruxolitinib. . Physical exam, vital signs, concomitant medication, adverse event reporting, CBC, CT scan of the abdomen, serum chemistry and BM aspirate and biopsy with cytogenetic analysis will be performed.

13.4 **Continuation Phase:** After completing cycle 4 response assessments, responders may continue to receive ruxolitinib and the final week 16 dose in the absence of DLT or disease progression. Bone marrow biopsy and aspirate will be

repeated after every 6 cycles (For patients who achieve CR, marrow CR, or PR a confirmation a one-time bone marrow aspirate and biopsy should be obtained 4 to 8 weeks after documentation of CR, marrow CR, or PR). A CBC will be obtained and complete metabolic profile as per standard of care. The End of Treatment assessment should be done within a week off treatment.

13.5 **End Of Treatment:** Patients discontinuing study early or any time after completing End of C4/Week 16 Response Assessment visit should complete their end of treatment visit within two weeks after their last dose of investigational product. Physical exam, vital signs, concomitant medication, adverse event reporting, CBC, CT scan of the abdomen, blood chemistry and BM aspirate and biopsy with cytogenetic analysis will be performed during the end of treatment visit. CT scan abdomen and BM aspirate and biopsy during EOT can be performed at the discretion of Coordinating Center PI.

13.6 **Off Treatment assessment:** includes best response achieved, date of first response, date of loss of response, reason for discontinuation.

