- d. In addition to specimen required for pathologic review, and additional aspirate will be collected (goal volume of 30cc). BM biopsy will occur at screening, end of Week 8, and Week 16. Week 8 and Week 16 BM biopsies have a window of +/- 14 days. In the event patient has CR or PR see Section 13.2.1 for additional one time BM biopsy.
- e. In addition to specimen required for routine labs, 6 green top vials, 1 red top vial.
- f. The Myeloproliferative Neoplasms Symptom Assessment Form (MPN-SAF TSS) using ERT's DiaryPro done by the patient. Data upload and device maintenance will occur at each scheduled visit through Week 16. Patient cannot be enrolled on the study protocol without ERT's DiaryPro registration. No waiver on the ERT handheld device will be given in any circumstances.
- g. BM aspirate and biopsy includes mutational panel should be performed every 6 cycles (window of +/- 14days) after completion of week 16 on the treatment.

h. CT scan abdomen may be completed with/without contrast.

i. Height is preferred to be recorded as a baseline; however, missing height during the screening process will not be a deviation on the study protocol.

*End of C4/ Week 16 Response Assessment and End of Treatment: Patients will complete a response assessment within one week after their last administration of ruxolitinib. Patients discontinuing study early should complete their end of treatment visit within two weeks after their last dose of investigational product. Physical exam, vital signs, concomitant medication, adverse event reporting, CBC, and serum chemistry and BM aspirate and biopsy with cytogenetic analysis will be performed.

**Continuation Phase: After completing cycle 4 response assessments, HI-platelet responders may continue to receive ruxolitinib and the final week 16 dose in the absence of DLT or disease progression. Bone marrow biopsy and aspirate will be repeated after every 6 cycles. A CBC will be obtained and complete metabolic profile as per standard of care. The off treatment assessment should be done within a week off treatment.

For patients who achieve CR, marrow CR, or PR a confirmation bone marrow aspirate and biopsy should be obtained 4 to 8 weeks after documentation of CR, marrow CR, or PR.

***Off Treatment assessment: includes best response, date of first response, date of loss of response, reason for discontinuation.

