Please rate your fatigue (weariness, tiredness) by circling the one number that best describes your fatigue right NOW	(No Fatigue) 0 1 2 3 4 5 6 7 8 9 10 (Worst Imaginable)
Please rate your fatigue (weariness, tiredness) by circling the one number that best describes your USUAL level of fatigue during past 24 hours	(No Fatigue) 0 1 2 3 4 5 6 7 8 9 10 (Worst Imaginable)
Please rate your fatigue (weariness, tiredness) by circling the one number that best describes your WORST level of fatigue during past 24 hours	(No Fatigue) 0 1 2 3 4 5 6 7 8 9 10 (Worst Imaginable)
Circle the one number that describes how, during the past 24 hours, fatigue has interfered with your	
• General activity	(Does not Interfere) 0 1 2 3 4 5 6 7 8 9 10 (Completely Interferes)
• Mood	(Does not Interfere) 0 1 2 3 4 5 6 7 8 9 10 (Completely Interferes)
• Walking ability	(Does not Interfere) 0 1 2 3 4 5 6 7 8 9 10 (Completely Interferes)
• Normal work (includes work both outside the home and daily chores)	(Does not Interfere) 0 1 2 3 4 5 6 7 8 9 10 (Completely Interferes)
• Relations with other people	(Does not Interfere) 0 1 2 3 4 5 6 7 8 9 10 (Completely Interferes)
• Enjoyment of life	(Does not Interfere) 0 1 2 3 4 5 6 7 8 9 10 (Completely Interferes)

© MD Anderson Cancer Center

Figure 1. The Myelofibrosis Symptom Assessment Form (MPN-SAF) Validation Survey.

**Myeloproliferative Neoplasm Symptom Assessment Form
(MPN-SAF) ©**

Circle the one number that describes how, during the past Week how much difficulty you have had with each of the following symptoms	
Filling up quickly when you eat (Early satiety)	(Absent) 0 1 2 3 4 5 6 7 8 9 10 (Worst Imaginable)
Abdominal pain	(Absent) 0 1 2 3 4 5 6 7 8 9 10 (Worst Imaginable)
Abdominal discomfort	(Absent) 0 1 2 3 4 5 6 7 8 9 10 (Worst Imaginable)
Inactivity	(Absent) 0 1 2 3 4 5 6 7 8 9 10 (Worst Imaginable)
Problems with headaches	(Absent) 0 1 2 3 4 5 6 7 8 9 10 (Worst Imaginable)
Problems with concentration - Compared to prior to my MPD	(Absent) 0 1 2 3 4 5 6 7 8 9 10 (Worst Imaginable)
Dizziness/ Vertigo/ Lightheadedness	(Absent) 0 1 2 3 4 5 6 7 8 9 10 (Worst Imaginable)
Numbness/ Tingling (in my hands and feet)	(Absent) 0 1 2 3 4 5 6 7 8 9 10 (Worst Imaginable)
Difficulty sleeping	(Absent) 0 1 2 3 4 5 6 7 8 9 10 (Worst Imaginable)
Depression or sad mood	(Absent) 0 1 2 3 4 5 6 7 8 9 10 (Worst Imaginable)
Problems with sexual desire or Function	(Absent) 0 1 2 3 4 5 6 7 8 9 10 (Worst Imaginable)

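### Do the symptom-score recording rules contradict each other, and does the lack of a named baseline and week-16 score call for a change?

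*Combined protocol and SAP*

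**What the plan says.** Section 14 (Symptom Assessment in CMML) sets nightly entry: "The subject will be instructed to complete the eDiary each night beginning on Day -4 or earlier of the screening phase". It gives the start and end as "eg, 4 days prior to Cycle 1 Day 1) through treatment discontinuation", and adds: "The subject will return the device and the docking station for the final time at the EOT visit".

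Section 13.1, on re-screening, says "Patient can be re-screened and start the first day of treatment on the same day" if eligible. Marrow and CT may be carried over, but "all the other procedures including labs, Myeloproliferative Neoplasms Symptom Assessments, research labs (research lab exclude aspirate) will be performed during the re-screening process".

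Study Calendar footnote f says: "Data upload and device maintenance will occur at each scheduled visit through Week 16". It also makes DiaryPro registration a condition of enrolment, with no waiver. A later calendar note allows a paper form at screening or re-screening visits when the electronic one is unavailable. Where the two differ, the treating physician chooses, for eligibility only.

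The score is used in three places:
- entry, at a total above 17 or with symptomatic splenomegaly (4.1.9);
- the secondary change from baseline to week 16 (1.2.4, 3.2.4);
- the symptom response in Section 14, a fall of at least 50% in those scoring 17 or more.

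The synopsis and Section 13.1 place the baseline form within four weeks of starting treatment. Section 13.6 collects "best response achieved, date of first response, date of loss of response". The symptom items in Appendix C ask about difficulty "during the past Week how much difficulty you have had with each of the following symptoms".

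**The concern.** A patient re-screened and dosed on the same day has no diary night between the two. If the score that admitted the patient also serves as baseline, selection on a high score makes the later score fall on average with no true change. A single-arm trial has no control group to show this.

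After week 16, Section 14 keeps the diary going while footnote f schedules no further upload. Loss of a symptom response might then go undated, although 13.6 asks for that date and duration of response is a secondary endpoint (3.2.3).

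The diary yields many scores, and no section names a night, an average or a minimum number of entries for either time point. Nightly entry on a one-week recall also makes neighbouring scores overlap. At stake would be bias in the mean symptom change and some room to choose the score after seeing the data.

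**Working it through.** **1. Before dosing.** Section 14 counts Day -4 back from Cycle 1 Day 1, not from the re-screening visit. A patient being re-screened has been screened before. If the diary runs from Day -4, there are four pre-dose nights (Days -4, -3, -2, -1); re-screening and first dose can then both fall on Day 1, and both sections are met. A count of zero nights arises only if nights after re-screening are the only ones counted, and neither section does that. Same-day start is also a permission, not the standard path. What is unsaid is whether diary nights from the first screening may serve as baseline.

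**2. After week 16.** Footnote f limits upload and device upkeep. Section 14 governs entry, which continues to treatment discontinuation, and has the device handed in at the end-of-treatment visit for archiving. Later entries can be recovered then. The calendar row also stops at Week 16 in the text available, but that table may be broken in extraction and is not relied on. The link to duration of response is not stated either: 3.1.1 does not name symptom response, and objective 1.2.3 points to the first secondary endpoint, which is AML transformation.

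**3. Which score.** The four-week baseline period is given. The choice among entries within it, and around week 16, is not.

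**4. Size.** The plan gives no score distribution, no measurement error and no test of the change, so there is no plan figure to reproduce. All inputs here are assumptions: true mean μ = 20 or 25, between-patient SD σ = 8 or 10, within-patient SD τ = 3, 5 or 7, no true change, entry if the score exceeds 17.

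With s = √(σ² + τ²) and z = (17 − μ)/s, the expected fall from an entry-score baseline is (τ²/s) × φ(z)/(1 − Φ(z)).

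- μ = 20, σ = 8, τ = 5: s = √89 = 9.434, z = −0.318, ratio 0.607; fall = (25/9.434) × 0.607 = 1.61.
- μ = 25, σ = 10, τ = 5: s = √125 = 11.18, z = −0.716, ratio 0.405; fall = (25/11.18) × 0.405 = 0.90.

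Simulation, with scores limited to 0–100 and nightly scores built as 7-day moving means, agrees:

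| τ | Fall, entry score as baseline | Average if 10–30% take the same-day path |
|---|---|---|
| 3 | 0.3–0.6 | 0.03–0.2 |
| 5 | 0.9–1.6 | 0.1–0.5 |
| 7 | 1.7–2.9 | 0.2–0.9 |

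The last column is the middle one times 0.1 to 0.3, for example 0.3 × 2.90 = 0.87. With a separate baseline the fall is about 0.

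Chance of a 50% fall at τ = 7:
- entry score against one week-16 score: 7.2–11.8%;
- separate single baseline of 17 or more against one week-16 score: 5.2–8.5% of those with such a baseline (4.4–6.4% if all symptom entrants are the denominator);
- 4-night baseline mean against 7-night week-16 mean: 3.2–5.2%.

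Suppose all 29 patients entered on symptoms and 30% started on the same day: 0.30 × 29 = 8.7 patients. At the upper ends, the excess chance responders are 8.7 × (11.8% − 8.5%) = 0.29 against a separate single baseline, and 8.7 × (11.8% − 5.2%) = 0.57 against averaged windows.

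**The case for a change.** The strongest case is that the missing derivation rule reaches beyond same-day starters. If the entry score were the baseline for every patient who entered on symptoms, the full fall of 0.3–2.9 points would apply, about 1–11% of the entry mean. A harsher illustration, with a fixed usual score of 18 or 25 and independent nightly errors of SD 4 to 8, gives chance responses of 0.3–23% for one night against one night, and 2–80% if the lowest of seven nights counted. The Study Reference Manual is cited for administering the diary, not for scoring it, and a rule written in advance costs little.

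Part of this stands. No section selects the entries, and the wording on collection after week 16 is loose. But the large figures need poor choices. The lowest night is not a natural reading of a week-16 value, and 7-night means bring the same illustration below 0.5%. Independent nights also sit badly with a one-week recall, although a 7-day recall for the whole score is itself an assumption, since the fatigue items in Appendix C ask about now and the past 24 hours.

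A written rule would also not remove the problem it targets. For a same-day starter with no earlier diary nights, the only pre-dose score is the re-screening score or a same-day repeat, so the selection effect stays.

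**Conclusion.** No change follows. The re-screening rule and the diary rule can both be met, and footnote f does not stop nightly entry. The mismatch after week 16 is a minor slip of wording. The unnamed baseline and week-16 scores are missing detail that an analyst can fill sensibly, from pre-dose diary nights and nights near the week-16 assessment that Section 14 already collects.

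For the same-day path the effect is under 1 point on average over patients who entered on symptoms, and under 0.6 of an expected chance responder among 29. It bears on a secondary endpoint with no planned test. No effect on the primary endpoint is shown, since 3.1.1 already counts stable disease. These sizes rest on assumed score distributions, a 10–30% share of same-day starters (30% for the responder count) and, for averaged windows, a 7-day recall. If the entry score were used as baseline for everyone, the spurious fall would be 0.3–2.9 points, which is worth remembering when the change is reported.

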15 STATISTICAL CONSIDERATIONS

15.1 Study Design

This will be a two stage Simon's phase 2 design. After testing the treatment dose on 10 patients in the first stage, the trial will be terminated if 1 or fewer achieve a clinical benefit. If the trial goes on to the second stage, a total of 29 patients will be studied. If the total number responding is less than or equal to 5, the drug is rejected.

15.2 Sample Size/Accrual Rate

The Simon's optimal two-stage design will be employed to test the null hypothesis that response rate (RR) is less than 10% versus the alternative that RR greater or equal to 30%. If the treatment is actually not effective, there is a 0.05 probability of concluding that it is. If the drug is actually effective, there is a 0.19 probability of concluding that it is not. The probability of early terminating the trial at the end of first stage under the null is 0.74. After testing the treatment dose on 10 patients in the first stage, the trial will be terminated if 1 or fewer desired respond. If the trial goes on to the second stage, a total of 29 patients will be studied. If the total number responding is less than or equal to 5, the drug is rejected. A sample size of 29 from Phase 2 produces a two-sided 95% CI with a width equal to 0.38 (± 19) when the sample proportion is 0.50 that is the maximum width for a CI with an given sample sizes.

15.3 Statistical Analysis Methods

Demographic and clinical variables for the study patients will be summarized using descriptive statistics (mean, standard deviation, median, inter-quartile range, range, and frequency counts and percentages). Safety and efficacy data will be analyzed overall as well as separately for each dose cohort when appropriate.

15.4 Safety Analysis

This analysis will include all patients who have received any protocol treatment, regardless of patient eligibility. The number (%) of patients with adverse events, serious adverse events, and adverse events leading to treatment discontinuation will be reported. Adverse events summary will be reported by type and severity. Laboratory parameters will also be summarized using descriptive statistics. The number and proportion of patients with DLTs will be summarized.

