6.3.1.5 Blood Products

The use of blood products to include packed red blood cells (PRBCs) and platelet transfusions are permitted and to be given at the discretion of the treating physician. Recommended guidelines for transfusion include a platelet threshold of 10,000/L for platelet transfusion and a hemoglobin threshold of 8g/dL for PRBC transfusion.

6.4 **Prohibited Medications**

Patients must abstain from using prohibited prescription or non-prescription drugs within 7 days or 5 half-lives (whichever is longer) prior to the first dose of study medication and until completion of follow-up procedures (Exclusion Criteria).

The following medications are prohibited during the study:

- Any prior or concomitant use of another JAK inhibitor.
- Any investigational medication other than the study drugs.
- Use of the potent inducers of CYP3A4, rifampin and St John's Wart, is not permitted at any time during participation in the study.
- The GM-CSF growth factor receptor agonists must not be used. Preclinical evidence suggests that it is important for CMML proliferation and survival and it is directly upstream for JAK2, the target of ruxolitinib. GM-CSF must not have been used for at least 28 days prior to receiving the first dose of study drug.

7 Duration of Therapy

Patients will be treated for a total of 16 weeks. For patients responding at week 16, treatment may continue until one of the following criteria applies:

- 7.1 Inter-current illness that prevents further administration of treatment,
- 7.2 Unacceptable adverse event(s),
- 7.3 Patient decides to withdraw from the study, or
- 7.4 General or specific changes in the patient's condition render the patient unacceptable for further treatment in the judgment of the investigator.
- 7.5 Evidence of disease progression by the IWG MDS/MPN criteria.

8 Duration of Follow-Up

Patients will be followed as per calendar on treatment for 17 weeks. After 17 weeks patient who continue on study will be followed monthly. Off study data on AML transformation and overall survival will be updated every 6 month or until death, whichever occurs first. Patients removed from study for unacceptable adverse events will be followed until resolution or stabilization of the adverse event.

9 Criteria for Removal from Study

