9.3 Subject Withdrawal from Study Medication

If the subject is permanently withdrawn from treatment with study medication, but does not withdraw consent, the investigator must make every effort to have the

subject complete all withdrawal assessments at the time of withdrawal, and complete all scheduled follow-up visits. Treatment with study medication must be discontinued if:

- The subject withdraws consent.
- Further participation would be injurious to the subject's health or well-being in the Investigator's medical judgment.
- The study is terminated.
- The subject becomes pregnant
- The patients exhibits leukemic transformation (as evidenced by bone marrow blast counts of at least 20%, or peripheral blast counts of at least 20% lasting at least 8 weeks.
- No clinical benefit has been attained after 16 weeks of treatment.
- Evidence of Disease progression according to IWG MDS/MPN criteria.
- a subject is significantly non-compliant with the requirements of the protocol.
- a subject has an adverse experience that would, in the investigator's judgment, make continued participation in the study an unacceptable risk.

Patients withdrawing from study can be tapered off of ruxolitinib over a 4 week period at the discretion of the investigator

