11.7 Time Period and Frequency of Detecting AEs and SAEs

The investigator or site staff is responsible for detecting, documenting and reporting events that meet the definition of an AE or SAE. AEs will be collected from the start of Investigational Product and through the follow-up contact. SAEs will be collected

over the same time period as stated above for AEs. However, any SAEs assessed **as related** to study participation (e.g., investigational product, protocol mandated procedures, invasive tests, or change in existing therapy) will be recorded from the time a subject consents to participate in the study up to and including any follow-up contact. All SAEs will be reported to INCYTE [contact] within 24 hours, as indicated.

11.8 Prompt Reporting of Serious Adverse Events and Other Events to the FDA with notification to INCYTE

Any serious adverse events which occur during the clinical study or within 30 days of receiving the last dose of study medication, whether or not related to the study drug, must be reported by the investigator. In addition, any SAEs which occur as a result of protocol specific diagnostic procedures or interventions must also be reported. SAEs brought to the attention of the investigator at any time after cessation of ruxolitinib and considered by the investigator to be related or possibly related to ruxolitinib must be reported to FDA with notification to INCYTE [contact] if and when they occur. Additionally, in order to fulfill international reporting obligations, SAEs that are related to study participation (e.g., procedures, invasive tests, change from existing therapy) or are related to a concurrent medication will be collected and recorded from the time the subject consents to participate in the study until he/she is discharged.

Type of Event	Initial Reports		Follow-up Information on a Previous Report	
	Time Frame	Documents	Time Frame	Documents
All SAEs	24 hours*	“SAE” data collection tool	24 hours*	Updated “SAE” data collection tool
Pregnancy	2 Weeks*	Pregnancy Notification Form	2 Weeks*	Pregnancy Follow-up Form

- From the time point when the SAE or pregnancy became known to reporter.

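### Section 15.4 summarises adverse events only as crude percentages of treated patients, although time on drug depends on response; a weeks 1–16 summary and an exposure summary should be added

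*Combined protocol and SAP*

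**What the plan says.** Section 15.4 defines the safety population as everyone treated: "This analysis will include all patients who have received any protocol treatment, regardless of patient eligibility". The measure is a count and a percentage: "The number (%) of patients with adverse events, serious adverse events, and adverse events leading to treatment discontinuation will be reported". The only breakdown of adverse events is this: "Adverse events summary will be reported by type and severity". The section also plans descriptive laboratory summaries and the number and proportion of patients with DLTs. Neither 15.4 nor 15.3 names a fixed window, a person-time rate, a cumulative incidence or a summary of treatment duration.

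Time on drug is set elsewhere. Section 7 gives the base period, "Patients will be treated for a total of 16 weeks", and then the extension: "For patients responding at week 16, treatment may continue until one of the following criteria applies". The criteria that follow are intercurrent illness, unacceptable adverse events, patient withdrawal, a change in the patient's condition, and progression. No maximum is given. Section 9.3 lists among the reasons for mandatory discontinuation: "No clinical benefit has been attained after 16 weeks of treatment".

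The observation window follows treatment. Section 11.7 says: "AEs will be collected from the start of Investigational Product and through the follow-up contact". No time is given for that contact. Section 11.8 requires reporting of "Any serious adverse events which occur during the clinical study or within 30 days of receiving the last dose of study medication".

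**The concern.** A crude percentage over all treated patients has a clear meaning when everyone is observed for about the same time. Here one group stops at week 16 because the drug did not help, another may stay on drug for many months because it did, and early deaths, progressions and withdrawals contribute only a few weeks. One denominator covers all three.

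This has two consequences. First, the reported percentage can move with efficacy while the underlying toxicity stays the same: more continuing patients means more time in which to have a first event. Early stopping pulls it the other way. Second, a patient taken off at week 16 for lack of benefit can no longer be counted as discontinuing because of an adverse event, so that percentage also depends on how many patients continue.

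What is at stake is interpretation. The primary efficacy endpoint is fixed at week 16 (Section 3.1.1), while the safety percentages have no common period. A reader who sets the two side by side could take the safety figures for the risk of 16 weeks of treatment, which they are not.

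**Working it through.** Section 15.4 states no figure to reproduce. The 10% and 30% used below as illustrative shares continuing are the null and alternative response rates of Section 15.2. That design reproduces: with stopping at 1 or fewer of 10 and rejection at 5 or fewer of 29, exact enumeration gives type I error 0.047, type II error 0.195 and early termination under the null 0.736, against the stated 0.05, 0.19 and 0.74.

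**Illustration 1**

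Assumptions, none of them in the documents: constant first-event hazard h per month; everyone treated to week 16 (16/4.345 = 3.68 months); a share f then continues for m further months; nobody else has a first event after week 16.

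- 16-week risk: R = 1 − exp(−h × 3.68)
- Crude percentage: R + f × (1 − R) × [1 − exp(−h × m)]

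For h = 0.05 and m = 12:

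- R = 1 − exp(−0.184) = 16.8%
- added risk if all continued = 0.832 × (1 − exp(−0.6)) = 0.832 × 0.451 = 37.5 points
- f = 0.10: 16.8 + 3.8 = 20.6%
- f = 0.30: 16.8 + 11.3 = 28.1%

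| h per month | further months | 16-week risk | crude, 10% continue | crude, 30% continue |
|---|---|---|---|---|
| 0.05 | 6 | 16.8% | 19.0% | 23.3% |
| 0.05 | 12 | 16.8% | 20.6% | 28.1% |
| 0.05 | 24 | 16.8% | 22.6% | 34.3% |
| 0.10 | 12 | 30.8% | 35.6% | 45.3% |

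**Illustration 2, a different parameterisation**

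Assume a week-16 risk q = 20% and total treatment of T weeks in those who continue. Crude percentage = (1 − f) × q + f × [1 − (1 − q)^(T/16)].

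- T = 52: 1 − 0.8^3.25 = 51.6%. The crude figure is 0.9 × 20 + 0.1 × 51.6 = 23.2% at f = 10%, and 0.7 × 20 + 0.3 × 51.6 = 29.5% at f = 30%.
- T = 24: 20.8% and 22.5%. T = 104: 25.7% and 37.0%.
- The week-16 incidence is 20% at every f. First events divided by time at risk is also unchanged: −ln(0.8)/16 × 52 = 0.725 per patient-year, or 72.5/12 = 6.0 per 100 patient-months.

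**Sensitivity (q = 20%, T = 52; f = 10% then 30%)**

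- Hazard after week 16 halved: 21.8% and 25.3%.
- Hazard after week 16 cut to a quarter: 20.9% and 22.8%.
- No hazard after week 16: 20.0% and 20.0%, so no effect.
- 20% of patients stop at week 8, hazard constant: 21.3% and 27.6%.
- 40% of patients stop at week 8, hazard constant: 19.4% and 25.7%. The first figure lies below the true 16-week risk.
- A very common event (q = 90%), hazard constant: 91.0% and 93.0%.

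**Scale against sampling error**

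The gap between 28.1% and 20.6% is 7.5 points, about 2.2 patients of 29. An observed 8/29 (28%) has an exact 95% interval of 13% to 47%.

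**The case against.** The strongest reply is that nothing here is wrong. Counts and percentages by type and severity correctly describe what happened to the treated patients. There is one arm, so no comparison between arms is distorted. The Simon rule uses response only. The protocol lists no safety objective or endpoint, and the dose came from the earlier phase 1 study. All of this stands, and it limits the point to a reporting improvement.

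Other parts of the plan also help. Section 10.1 records the date and reason for stopping drug and will summarise the reasons, so stops for adverse events will appear beside other stops. The study calendar says adverse events are summarised and reported before each cycle, and Section 17.6 provides regular safety review. These support monitoring and partly meet the concern about discontinuations. None of them puts a fixed-window or exposure-based analysis into Section 15.

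The size is open to challenge. The hazard and the further months are assumptions, and the effect disappears if toxicity is early. The share continuing is uncertain too. Section 7 speaks of responding patients, the synopsis of patients receiving clinical benefit, and a calendar footnote of HI-platelet responders only, while the primary endpoint counts stable disease. At n = 29 the shift is smaller than the sampling error. That is fair, but a confidence interval neither shows nor removes a shift caused by unequal follow-up.

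A reader might infer more than the text supports:

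- That the percentages cannot be compared with the earlier phase 1/2 study. Section 2.5 gives neither exposure nor the adverse event method of that study, so this cannot be judged.
- That the week-16 table should replace the whole-period table as the main one. That would push late toxicity, and events during the taper of up to 4 weeks allowed in Section 9.3, into the background.
- That a competing-risk analysis of discontinuation is required. With few such events among 29 patients it would add little.

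**Conclusion.** The point holds as a cheap improvement. Section 15.4 offers only crude percentages, and both time on drug and adverse event observation depend on outcome. The percentages are valid counts, but they are not a 16-week risk, and they can rise with the proportion who continue.

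The size cannot be determined from the documents. Moving the share continuing from 10% to 30% shifts the crude figure by 7.5 points under a constant hazard of 0.05 per month and 12 further months. With q = 20%, the shift is 1.7 points if continuing patients are treated to week 24 and 11.3 points if treated to week 104. It is zero if all first events fall in the first 16 weeks. The plan as written would not show which of these applies.

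It would be too strong to call the safety results biased or the trial's conclusion unsafe. The sample size, the stopping rule and the efficacy analysis are untouched.

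**What to change.** Keep the crude whole-period table by type and severity, and add three items to Section 15.4:

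1. The same categories (adverse events, serious adverse events, discontinuations for adverse events) with onset from first dose to week 16, with the number of patients still on drug.
2. A summary of treatment duration and total exposure.
3. Whole-period events per 100 patient-months. State whether first events or all events are counted, and match the time at risk to that choice.

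Late-onset and post-treatment events, including those during any taper, stay in the whole-period table.

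The cost is SAP wording and a few table columns. Section 10.1 already records the drug discontinuation date. First-dose and event onset dates are assumed to be captured, since the documents do not list them explicitly. The downside is a second set of safety figures, and rates that are simplest to interpret only when the hazard is roughly constant.
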